### **9.9.4 Clinical Laboratory Evaluations**

Clinical laboratory evaluations including chemistry (fasted at least 10 hours), CBC, and UA will be collected as outlined in the respective Schedules of Study Procedures (double-blind, [Table 2](#); open-label, [Table 3](#); placebo-controlled 24-week histology, [Table 4](#)).

Laboratory assessments of fasted lipid panel (total cholesterol, LDL, HDL, and TG), lipoprotein particles, HbA1c, insulin, HOMA-IR, and FFAs will be performed as outlined in the respective Schedules of Study Procedures (double-blind, [Table 2](#); open-label, [Table 3](#); placebo-controlled 24-week histology, [Table 4](#)). For the placebo-controlled 24 week histology, test results will be monitored by the sponsor's medical monitor/designee, but are blinded to the site and subject for ALT, AST, Total Cholesterol, LDL, HDL and triglycerides for Week 2 – Week 30 sample collections. LDL-direct may be used if LDL-C was not able to be analyzed.

Laboratory assessments for C4 and serum bile acids will be performed as outlined in the respective Schedules of Study Procedures (double-blind, [Table 2](#); open-label, [Table 3](#); placebo-controlled 24-week histology, [Table 4](#)).

Laboratory assessments for changes in bile-mediated absorption as measured by vitamin D and INR will be performed as outlined in the respective Schedules of Study Procedures (double-blind, [Table 2](#); open-label, [Table 3](#); placebo-controlled 24-week histology, [Table 4](#)).

Cytokines (IL-6, and TGF- $\beta$ ) and hs-CRP will be assessed as outlined in the respective Schedules of Study Procedures (double-blind, [Table 2](#); open-label, [Table 3](#)).

Hepatitis screen and HIV antibody screen will be performed at Screening.

A urine screen for drugs of abuse will be performed at Screening.

A stool sample will be collected at Day 1 and Week 12 in only the double-blind and open-label single-blind cohorts. Stool samples will be analyzed for microbiome (bacterial composition) and fecal fat content (double-blind, [Table 2](#); open-label, [Table 3](#)).

A serum qualitative pregnancy test (all female patients of child bearing potential) will be performed at Screening and Week 24/EOT and Week 30/EOS. A urine pregnancy test (all female patients of child bearing potential) will be performed at Day 1 (pre-dose).

AFP will be measured at Screening.

Samples for analysis of ADAs, NAbS, and exploratory biomarkers will be collected as outlined in the respective Schedules of Study Procedures (double-blind, [Table 2](#); open-label, [Table 3](#); placebo-controlled 24-week histology, [Table 4](#)). All NAb samples will be collected as scheduled, and analyzed only if necessary based on ADA results.

Exploratory biomarkers, ELF panel, [REDACTED] will be assessed as outlined in the respective Schedules of Study Procedures (open-label, [Table 3](#); placebo-controlled 24-week histology, [Table 4](#)).

Processing, storage, and shipping instructions for the above will be presented in a separate Lab Manual.

#### **9.9.5 12-Lead Electrocardiograms**

12-lead ECGs will be performed after the subject has been supine for at least 5 minutes, and as outlined in the respective Schedules of Study (double-blind, [Table 2](#); open-label, [Table 3](#); placebo-controlled 24-week histology, [Table 4](#)).

#### **9.9.6 Vital Signs**

Vital signs (including temperature, respiratory rate, and seated blood pressure and pulse) will be obtained at Screening and at all study visits as outlined in the respective Schedules of Study Procedures (double-blind, [Table 2](#); open-label, [Table 3](#); placebo-controlled 24-week histology, [Table 4](#)).

Seated blood pressure and pulse will be measured after the subject has been seated for at least 5 minutes.

#### **9.9.7 Physical Examinations**

A routine physical examination will be performed at selected study visits in each of the cohorts as outlined in the Schedule of Study Procedures (double-blind, [Table 2](#); open-label, [Table 3](#); placebo-controlled 24-week histology, [Table 4](#)).

### **9.9.8      Weight, Body Mass Index, and Waist Circumference Measurements**

Subjects will be weighed, BMI calculated, and waist circumference measured at Screening, and selected study visits as outlined in the Schedule of Study Procedures (double-blind, [Table 2](#); open-label, [Table 3](#); placebo-controlled 24-week histology, [Table 4](#)). Formal instructions for recording weight and measuring waist circumference will be provided to sites.

### **9.9.9      Local Injection-Site Symptom Assessments (LISSA)**

Injection-site evaluation will be made and documented (including photographs, as needed) by the PI or clinic staff using a LISSA ([Appendix B](#)).

The LISSA is to be administered pre- and post-dose (approximately 20 minutes after injection) at Day 1 through EOT in the double-blind and open-label single-blind cohorts. A single assessment will be performed at the Week 16 (double-blind cohort) or Week 18 (open-label single-blind cohort), to assess any prior dose injection site reactions.

For the placebo-controlled 24-week histology cohort, LISSA evaluations are to be performed at each clinic visit from Day 1 through Week 30.

The instructions below are to be followed for the pre-dose LISSA:

- The injection site area(s) should be examined for any ISRs at every visit.
- If a single ISR is observed, the LISSA should be used to rate that ISR.
- If multiple ISRs are observed, the LISSA should be used to rate the most severe ISR.
- The study visit note should document the total number of ISRs seen on examination.

The LISSA is intended to be a “snapshot” of the ISRs at the time of clinic assessment. The LISSA is not intended to capture ISR data (frequency, severity, duration, etc.) in between clinic visits. As with any other potential AE, Investigator judgment should be used as to whether any ISR is recorded as an AE. Mild to Severe Reactions (LISSA Grades 1–3) are reported as AEs at the discretion of the investigator unless standard SAE criteria are met and then must be reported as an SAE. Life-threatening (LISSA Grade 4) meet SAE criteria and must be reported as such.

LISSAs may be performed if necessary and as clinically indicated by the PI to capture ISRs outside of the routine scheduled assessment time points.

The 2007 FDA Toxicity Grading Scale ([Appendix B](#)) will be used to assess any ISRs ([U.S. Department of Health and Human Services 2007](#)). The documented record will include all of the symptoms, severity, and any local reaction (including pain, tenderness, redness, and swelling) and size of injection-site skin reactions identified and observed by the subject or clinic personnel. LISSA scores will be documented on the subject’s CRF.

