## 11 Adverse Events

### 11.1 Definition and Grading Intensity of Adverse Events

An AE is defined as any untoward medical occurrence in a subject of clinical investigational participation administered a pharmaceutical product, whether or not considered drug related. A TEAE is an AE that is reported after a dose of study drug.

AEs include the following:

- Unfavorable changes in general condition
- Subjective or objective signs/symptoms
- Concomitant diseases or accidents
- Clinically relevant adverse changes in laboratory parameters observed in a subject in the course of a clinical study

AEs comprise all disturbances of general health status, subjective and objective disease symptoms (including laboratory abnormalities), and accidents observed in the context of a clinical trial, irrespective of a possible causal relationship with the administration of the trial substance. Events occurring in the framework of a clinical trial during drug-free and post-treatment periods or under placebo are also to be designated as AEs.

All AEs regardless of how identified (e.g., volunteered, elicited, noted on physical examination) will be recorded throughout the study from the time the patient signs informed consent through Follow-up.

Subjects will be followed for resolution of AEs, by querying the subjects for an ongoing AE until resolved or until any unresolved AEs are judged by the PI to have stabilized or if lost to follow-up. Resolution of all AEs will be promptly documented by the clinic on the subject's CRF.

Any pregnancy diagnosed during the study must be reported immediately to the PI and Sponsor, including pregnancy in female partners of male subjects. The pregnancy will be followed to term and/or outcome and this outcome must be reported to the Sponsor.

Pregnancy, in and of itself, is not regarded as an AE or SAE unless the birth results in a congenital anomaly/birth defect or there is suspicion that the study medication may have interfered with the effectiveness of a contraceptive medication or method.

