The PI will rate the severity of AEs using the CTCAE v4.03 to grade the severity. Each CTCAE v4.03 term is a Medical Dictionary for Regulatory Activities (MedDRA) Lowest Level Term (LLT). The CTCAE displays Grades 1 through 5 with unique clinical descriptions of severity for each AE. Not all Grades are appropriate for all AEs. Therefore, some AEs are listed with fewer than five options for Grade selection. Grade 5 (Death) is not appropriate for some AEs and, therefore, is not an option.

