## 11.2 Criteria for Determining Relationship to Drug

The PI will make a blinded determination of the relationship of the AE to NGM282 (including placebo) in the double-blind cohort. An open-label determination of the relationship of the AE to NGM282 and a separate open-label determination of the relationship of the AE to rosuvastatin will be made in the open-label single-blind cohort. The PI will make a blinded determination of the relationship of the AE to NGM282 (including placebo) and a separate open-label determination of the relationship of the AE to rosuvastatin in the placebo-controlled 24-week histology cohort. All determinations of relationship will be made using a four-category system (not related, possible, probable, or definite) according to the following guidelines:

- **NOT RELATED** = an AE that does not follow a reasonable temporal sequence from administration of the drug and that can be reasonably explained by other factors, including underlying disease, complications, concomitant drugs, or concurrent treatment;
- **POSSIBLE** = an AE that follows a reasonable temporal sequence from the administration of the drug (including the course after withdrawal of the drug) and that cannot be excluded as being possibly caused by the drug (e.g., existence of similar reports attributed to the drug and/or its analogues; reactions attributable to the pharmacological effect of the drug), although other factors such as underlying disease, complications, concomitant drugs, or concurrent treatment are presumable;
- **PROBABLE** = an AE that follows a reasonable temporal sequence from administration of the drug (including the course after withdrawal of the drug) and that can be excluded as being possibly caused by other factors, such as underlying disease, complications, concomitant drugs, or concurrent treatment.
- **DEFINITE** = an AE that follows a reasonable temporal sequence from administration of the drug (including the course after withdrawal of the drug), follows a known or hypothesized cause–effect relationship, and (if appropriate) satisfies the following:
  - Positive results obtained in drug sensitivity tests
  - Toxic level of the drug present in blood or other body fluids

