### **12.10.1 Adverse Events**

AEs, including serious AEs, will be coded using the MedDRA. The number and percentage of subjects experiencing an AE will be summarized for each system organ class (SOC) and preferred term (PT) by treatment group. In addition, AEs will be tabulated according to intensity, causality, and relation to the study drug. Individual data listings for AEs will be presented for each subject.

All AE summaries will be restricted to TEAEs only. TEAEs are defined as AEs that commence on or after the time of start of first study-drug administration. AEs without an onset date or time will be defined as treatment emergent, except if an incomplete date (e.g., month and year) clearly indicates that the event started prior to the start of first administration of study drug or if the AE stop date indicates that the event started or stopped prior to the start of first administration of study drug.

For the summaries of AEs, subjects who experience the same AE (in terms of the MedDRA preferred term) more than once will be counted only once for that event. Separate summaries will be provided for AEs by intensity, causality, and relationship to study drug.

All AEs will be listed. SAEs will be summarized and listed.

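### Protocol 9.9.9 leaves AE entry of a non-serious severe (LISSA Grade 3) injection-site reaction to the investigator, and one that is not entered cannot count toward the mandatory triggers in 8.2 and 7.1

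*Protocol*

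**What the plan says.** Protocol 9.9.9 has injection sites scored on the 2007 FDA scale reproduced in Appendix B. On whether a scored reaction also becomes an adverse event, it says: "As with any other potential AE, Investigator judgment should be used as to whether any ISR is recorded as an AE". It then names the grades: "Mild to Severe Reactions (LISSA Grades 1–3) are reported as AEs at the discretion of the investigator unless standard SAE criteria are met". Only Grade 4, or a reaction of any grade that meets the SAE criteria, must be reported.

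Protocol 11.1 sets the general rule. "An AE is defined as any untoward medical occurrence in a subject of clinical investigational participation administered a pharmaceutical product", whether or not it is thought to be drug related, and "All AEs regardless of how identified (e.g., volunteered, elicited, noted on physical examination) will be recorded throughout the study". For severity, "The PI will rate the severity of AEs using the CTCAE v4.03 to grade the severity". Section 11.2 then has the investigator judge the relationship of each AE to NGM282.

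Two mandatory rules depend on these judgements. Section 8.2 stops a subject's treatment for a single related Grade 3 TEAE. Section 7.1 ends the entire study once there are three related Grade 3 or 4 TEAEs in one CTCAE category. SAP 9.2 restricts the AE summaries to TEAEs and includes a table of those of CTCAE grade 3 or higher.

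**The concern.** A discretionary entry step comes before two safety rules that are otherwise mandatory. Appendix B Grade 3 is not trivial. It covers pain that needs a narcotic or stops daily activity, tenderness with significant discomfort at rest, and redness or swelling wider than 10 cm. Most of these would ordinarily be untoward occurrences within 11.1, yet 9.9.9 names this grade among those the investigator may leave out.

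At stake is whether each severe local reaction receives a recorded severity grade and causality call. If some do not, the counts behind 8.2, 7.1 and the SAP Grade 3 or higher table depend partly on each site's entry habits. Section 5.1.3 reports injection-site reactions as the most common drug-related AEs in Phase 1, and section 5.4 gives fewer such reactions as one reason for choosing 1 mg over 3 mg. Consistent recording across the roughly 10 sites of the 24-week cohort is therefore worth having.

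**Working it through.** The plan states no figure on this point and none can be derived, so the check sets the provisions side by side.

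1. **Which reactions are discretionary.** Under 9.9.9, Grades 1 to 3 are discretionary unless SAE criteria are met. The gap is therefore confined to *non-serious* Grade 3 reactions.

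2. **Does such a reaction fit the AE definition?** Section 11.1 covers any untoward occurrence and expressly includes subjective or objective signs and symptoms. Pain needing a narcotic, or significant discomfort at rest, would normally qualify.

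3. **What AE status controls.** CTCAE grading (11.1) and relatedness (11.2) are specified for AEs. A LISSA score is neither: it uses a different scale and carries no causality call.

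4. **Can it be a TEAE without being an AE?** No, under either definition. Section 11.1: "A TEAE is an AE that is reported after a dose of study drug". Section 12.10.1: "TEAEs are defined as AEs that commence on or after the time of start of first study-drug administration". Both begin from an AE. SAP 9.2 does the same.

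5. **What the rules count.** Section 8.2 speaks of categories being observed, but the listed item is a related Grade 3 TEAE. Section 7.1 counts related Grade 3 or 4 TEAEs by CTCAE category. The SAP table counts TEAEs by CTCAE grade. None of them uses a LISSA grade. A non-serious LISSA Grade 3 reaction that is not entered as an AE therefore cannot count in any of the three.

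6. **What still captures it.** LISSA scores go on the CRF. They are tabulated by treatment group and time point (Protocol 12.10.7; SAP 9.6) and listed (SAP 18). This capture has limits. Section 9.9.9 describes the LISSA as a picture at the clinic visit, not a record of what happens between visits. Dosing is daily and mostly at home, and the later on-treatment visits in the 24-week cohort (Weeks 12, 18 and 24) are six weeks apart. An extra LISSA may be done when clinically indicated, but SAP 6.1 generally lists unscheduled data without summarizing them. For a severe reaction between visits, AE entry is the main route into a summary table.

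7. **How often.** The documents give no Grade 3 rate and no rate at which reactions are entered as AEs. What they do say points low: mild to moderate reactions in Phase 1, mainly at higher doses and larger volumes; mild reactions in the type 2 diabetes study (both 5.1.3), although 5.4 notes a trend to more frequent and more severe ones at 10 mg; and fewer reactions at 1 mg than at 3 mg (5.4). The 24-week cohort has up to 75 subjects, 50 of them on 1 mg. Any probability of a missed trigger would rest wholly on assumed rates, so none is given.

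**The case against.** The strongest reply is that 9.9.9 and 11.1 can be read together. The discretion in 9.9.9 is introduced as the judgement used for any potential AE, so it may only restate the ordinary question of whether something is an AE. A reader might infer a flat contradiction between the sections; the text supports only a tension. It is sharpest at Grade 3 because 9.9.9 names that grade and exempts only serious events.

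Second, part of the gap is already closed. The SAE criteria in 11.3 include substantial disruption of normal life functions and important medical events, so some disabling Grade 3 reactions must be reported anyway. That narrows the gap but leaves the non-serious ones.

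Third, a reader might infer that a site could omit a severe reaction without any protocol deviation. That is not established: an investigator applying 11.1 strictly would enter it, and an omission could be held to breach 11.1.

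Fourth, a reader might infer that nothing could then stop treatment. Section 7.1 also lets the sponsor stop an arm or the study for medical or ethical reasons, and 8.3 lets the investigator withdraw a subject in the subject's interest. These powers remain, but they are discretionary, whereas the 8.2 and 7.1 triggers are mandatory.

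Fifth, Grade 3 can be met by redness over 10 cm with no functional effect, on a scale written for healthy vaccine volunteers. Since 8.2 and 7.1 are strict, clinical judgement before they apply is defensible. That argues against making LISSA Grade 3 a trigger in itself. It does not argue against recording the reaction and letting the investigator grade it.

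Finally, entry moves the judgement rather than removing it, because the same investigator assigns grade and causality. That is correct and limits what the fix achieves.

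**Conclusion.** The point stands in a limited form. A non-serious LISSA Grade 3 reaction may be left out of the AE record under 9.9.9, and if it is, it receives no CTCAE grade or relatedness call and cannot count under 8.2, 7.1 or the SAP Grade 3 or higher table.

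Two further inferences are not supported. A reader might take LISSA Grade 3 to be CTCAE Grade 3, so that each omission is a missed stop. The documents give no mapping between the scales, and a reaction that was entered could be graded lower or judged unrelated. A reader might also think severe reactions vanish from the trial's data. Those seen at an assessment stay in the LISSA record, so the LISSA comparison of local tolerability between arms does not depend on AE entry.

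The effect is of unknown size and probably small at 1 mg. That expectation rests on the reactions described in 5.1.3 and 5.4, not on any reported Grade 3 rate. No efficacy analysis is affected. Severity is low; the case for change is that it costs little and sits ahead of mandatory safety rules.

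**What to change.** Amend 9.9.9 so that every LISSA Grade 3 reaction is entered as an AE, with a CTCAE v4.03 grade and a relatedness judgement assigned by the investigator. Keep investigator discretion for Grades 1 and 2, keep Grade 4 as it is, and leave 8.2 and 7.1 unchanged. A reaction graded below CTCAE 3 or judged not related would then trigger neither rule, but the judgement would be on record.

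The cost is one sentence in the protocol and matching CRF guidance. It brings a few more AE entries and possibly a higher reported rate of injection-site AEs. Any entry graded CTCAE 3 and related would stop that subject's treatment and count toward ending the study, which is what those rules already intend.

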## **10 Study Drug**

### **10.1 Clinical Supplies**

#### **10.1.1 NGM282**

NGM282 is formulated in aqueous isosmotic buffer solution with 0.01% polysorbate-20. It is filled into 1-mL, type I glass syringes, with a 29-g staked needle, needle shield, grey rubber plunger, and plastic plunger rod. Filled syringes are labeled and packaged into trays and cardboard cartons.

In the double-blind cohort, NGM282 is provided as a sterile solution for injection in a single-use, pre-filled syringe for SC administration at doses of 3 and 6 mg, and volume-matched placebo. In the single-blind cohort, NGM282 is provided as a sterile solution for injection in a single-use, pre-filled syringe for SC administration at doses of 0.3, 1, and 3 mg. In the placebo-controlled 24-Week histology cohort NGM282 is provided as a sterile solution for injection in a single-use, pre-filled syringe for SC administration at 1 mg dose and volume-matched placebo.

The drug product is manufactured for NGM under current Good Manufacturing Practice regulations [REDACTED]

[REDACTED] that has undergone FDA inspection.

#### **10.1.2 Rosuvastatin**

##### **10.1.2.1 Drug Supply for Open-Label Single-Blind Cohort**

For the open-label single-blind cohort, rosuvastatin will be supplied as 20-mg pink, round, convex-shaped, coated tablets with "RU20" on one side and blank on the other side in bottles of 30 tablets (NDC 16252-617-30). The active ingredient is rosuvastatin calcium and inactive ingredients include microcrystalline cellulose, lactose monohydrate, sodium carbonate monohydrate, sodium lauryl sulfate, crospovidone, magnesium stearate, titanium dioxide, polyethylene glycol, polyvinyl alcohol, talc, ferric oxide yellow, ferric oxide red, FD&C Red 40, and indigotindisulfonate sodium.

##### **10.1.2.2 Drug Supply for Placebo-Controlled 24-Week Histology Cohort**

For the placebo-controlled 24-week histology cohort, rosuvastatin will be supplied. Rosuvastatin calcium tablets 20 mg are light pink colored, round, biconvex, film coated tablets debossed with '1181' on one side and plain on other side in bottles of 90 tablets (NDC 13668-181-90). The active ingredient is rosuvastatin calcium and inactive ingredients include crospovidone, hypromellose, lactose monohydrate, magnesium stearate, microcrystalline cellulose, titanium dioxide, triacetin and ferric oxide red.

